1.0 INTRODUCTION

[figure not shown]
1.1 Background

Urticaria, also known as hives, is a common dermatologic condition which presents with the rapid appearance of pale to brightly colored wheals of various sizes ranging from several millimeters to several centimeters, with or without surrounding erythema, pruritus or occasional burning sensations, and the skin returning to normal typically within one to twenty-four hours (1) (2). The pathophysiologic mechanism involves the release of histamine and other mediators from mast cells and basophils; release in the dermis results in urticaria while release in the deeper dermis and subcutaneous tissues results in angioedema (2). Most commonly, symptoms are caused by exposure to allergens, foods, insect venom, medications, and viral infections. Persons of any ages may present with urticaria, with a lifetime prevalence of between 15% and 25% (2) (3)(4).

Acute urticaria is defined as urticaria persisting less than 6 weeks, whereas chronic urticaria persists 6 weeks or longer (2)(5)(6). Second-generation H1 antihistamines are first-line medication for the treatment of acute urticaria. In some cases, they may be titrated to two or even four times the normal dose to control symptoms followed by H2 antihistamines and corticosteroid for severe cases (1)(2). Indication for epinephrine includes emergency treatment of type 1 hypersensitivity reactions (7) and epinephrine injection is recommended in medical prescribing guidelines in the United States (US) for the management of acute flares with associated angioedema in patients with urticaria. Acute urticaria is treated with but often unresponsive to antihistamines and corticosteroids. Intramuscular (IM) epinephrine is typically efficacious in alleviating urticarial flares.

Epinephrine, illustrated in Figure 1 below, is a sympathomimetic catecholamine. Chemically, epinephrine is B-(3, 4dihydroxyphenyl)-a-methyl-aminoethanol. Epinephrine solution deteriorates rapidly on exposure to air or light, turning pink from oxidation to adrenochrome and brown from the formation of melanin. It is a colorless to light yellow crystalline compound, insoluble in water. The formula is $C_9H_{13}NO_3$ and the molecular weight is 183.20442.

Figure 1: Epinephrine

ARS Pharmaceuticals, Inc. (ARS) is investigating an epinephrine nasal spray (ARS-1) for patients with urticaria as a needleless alternative route of epinephrine administration for the treatment of urticarial flares.

ARS-1 is a novel formulation that includes a proprietary functional excipient called Intravail® A3 (dodecylmaltaside or DDM). DDM is a GRAS (Generally Recognized As Safe) excipient that is being evaluated in low concentrations (less than 1%) to improve the bioavailability of drugs administered by the intranasal (IN) route. The absorption enhancing properties of alkylglycoside surfactants, such as DDM, are believed to occur via loosening of the tight junctions (paracellular) coupled with the fluidization and penetration of cell membranes (transcellular) causing increased drug movement into the cell (8).

1.2 Clinical Experience with ASR-1 1.0 mg in Healthy Volunteers

ARS-1 1.0 milligram (mg) has been tested in in a series of PK studies to evaluate the bioavailability and bioequivalence of the IN formulation versus IM injections in both healthy volunteers and in volunteers with histories of seasonal allergies and rhinitis (Table 1).

Table 1: Summary of Individual Studies Included in the Integrated Pharmacokinetic Analysis

| STUDY | DESCRIPTION | TREATMENTS INCLUDED IN THE ANALYSIS | SUBJECTS |
|------------|-------------|-------------------------------------|------------|
| [REDACTED] | [REDACTED] | [REDACTED] | [REDACTED] |
| [REDACTED] | [REDACTED] | [REDACTED] | [REDACTED] |
| [REDACTED] | [REDACTED] | [REDACTED] | [REDACTED] |
| [REDACTED] | [REDACTED] | [REDACTED] | [REDACTED] |

1.2.1 Pharmacokinetics of ARS-1 1.0 mg in Healthy Volunteers

[REDACTED]

[REDACTED]

[REDACTED]

[REDACTED]

1.2.1.1 Concentration vs Time Curves – Integrated Analysis

[REDACTED]

[REDACTED]

[REDACTED]

1.2.1.2 Pharmacokinetics Parameters – Integrated Analysis

A summary of key PK parameters is provided in [Table 2](#).

[REDACTED]

[REDACTED]

[REDACTED]

[REDACTED]

[REDACTED]

[REDACTED]

Table 2: Comparison of Pharmacokinetics Parameters

| Product | N | C _{max} (pg/mL) Geometric Mean (CV%) | AUC _{0-t} (min*pg/mL) Geometric Mean (CV%) | Median T _{max} (minutes) (range) |
|------------|------------|---|---|---|
| [REDACTED] | [REDACTED] | [REDACTED] | [REDACTED] | [REDACTED] |
| [REDACTED] | [REDACTED] | [REDACTED] | [REDACTED] | [REDACTED] |
| [REDACTED] | [REDACTED] | [REDACTED] | [REDACTED] | [REDACTED] |
| [REDACTED] | [REDACTED] | [REDACTED] | [REDACTED] | [REDACTED] |

1.2.2 Pharmacodynamics of ARS-1 1.0 mg in Healthy Volunteers

Pharmacodynamic (PD) measurements included systolic blood pressure (SBP), diastolic blood pressure (DBP), and pulse rate (PR).

[REDACTED]

1.2.2.1 Systolic Blood Pressure – Integrated Analysis

[REDACTED]

[REDACTED]

[REDACTED]

[REDACTED]

Table 3: Systolic Blood Pressure by Treatment

| Treatment | N | E _{max} Mean (SD) | T _{E_{max}} Median (Range) |
|------------|------------|-------------------------------|--|
| [REDACTED] | [REDACTED] | [REDACTED] | [REDACTED] |
| [REDACTED] | [REDACTED] | [REDACTED] | [REDACTED] |
| [REDACTED] | [REDACTED] | [REDACTED] | [REDACTED] |
| [REDACTED] | [REDACTED] | [REDACTED] | [REDACTED] |

1.2.2.2 Diastolic Blood Pressure – Integrated Analysis

The mean change from baseline DBP versus time is presented in [Table 4](#). Summaries of PD parameters (E_{max} and T_{E_{max}}) are presented in [Figure 4](#).

[REDACTED]

[figure not shown]

Table 4: Diastolic Blood Pressure by Treatment

| Treatment | N | E _{max} Mean (SD) | T _{E_{max}} Median (Range) |
|------------|------------|-------------------------------|--|
| [REDACTED] | [REDACTED] | [REDACTED] | [REDACTED] |
| [REDACTED] | [REDACTED] | [REDACTED] | [REDACTED] |
| [REDACTED] | [REDACTED] | [REDACTED] | [REDACTED] |
| [REDACTED] | [REDACTED] | [REDACTED] | [REDACTED] |

1.2.2.3 Pulse Rate – Integrated Analysis

The mean change from baseline PR versus time is presented in [Figure 5](#). Summaries of PD parameters (E_{max} and T_{E_{max}}) are presented in [Table 5](#).

[REDACTED]

[figure not shown]

Table 5: Pulse Rate Pharmacodynamic Parameters by Treatment

| Treatment | N | E _{max} Mean (SD) | T _{E_{max}} Median (Range) |
|------------|------------|-------------------------------|--|
| [REDACTED] | [REDACTED] | [REDACTED] | [REDACTED] |
| [REDACTED] | [REDACTED] | [REDACTED] | [REDACTED] |
| [REDACTED] | [REDACTED] | [REDACTED] | [REDACTED] |
| [REDACTED] | [REDACTED] | [REDACTED] | [REDACTED] |

1.2.3 Overall Pharmacological Conclusions

[REDACTED]

1.2.4 Safety

1.2.4.1 Clinical Experience with ARS-1 in Adult Subjects

To date, more than 300 subjects have been exposed to ARS-1 with doses from 0.3 mg up to 4 mg. Most of the events were mild and there were no serious adverse events (SAEs) reported.

Table 6: Frequency of Expected Adverse Events for ARS-1[illegible]

| System Organ Class Preferred Term | Serious | Severity Grade ¹ | | | | | Incidence ² (n) | Incidence (%) |
|--------------------------------------|---------|-----------------------------|---|---|---|---|-------------------------------|------------------|
| | | 1 | 2 | 3 | 4 | 5 | | |
| | | | | | | | | |

¹ Grade: 1 = mild; 2 = moderate; 3 = severe; 4 = life-threatening; 5 = death

² Total number of subject (N) = 345

1.2.4.2 Clinical Experience with ARS-1 in Pediatric Subjects

1.3 Study Rationale

Both IM and SC dosing of epinephrine are approved by the FDA as efficacious in product labeling in the US.

An epinephrine nasal spray (ARS-1) is being developed for patients with urticaria as a needleless alternative route of epinephrine administration for the treatment of acute urticaria.

In previous studies, a 10 mg/mL formulation of ARS-1 administered as a 0.1 mL spray (2 mg total epinephrine dose) gave pharmacokinetics that were similar to a 0.3 to 0.5 mg injection products in the anterolateral thigh. The objective of this study is described in [Section 2.0](#).

2.0 STUDY OBJECTIVES

2.1 Study Objectives

IM epinephrine injection is indicated in the emergency treatment of allergic reactions (Type I) including anaphylaxis. Both IM and SC dosing of epinephrine is approved by the FDA as efficacious in product labeling in the US. Epinephrine injection is also recommended in medical prescribing guidelines in the US for the management of acute flares with associated angioedema in patients with urticaria. Acute urticaria is typically treated with but often unresponsive to antihistamines and corticosteroids. IM epinephrine is typically efficacious in alleviating urticarial flares. An epinephrine nasal spray (ARS-1) is being developed for patients as a needleless alternative route of epinephrine administration for the treatment of acute urticaria.

| Objective | Endpoints |
|--|--|
| Primary | |
| 
To determine the effect of ARS-1 versus placebo based on a patient reported pruritus/hive score
 
To assess time to effect and duration of effect on acute flares associated with urticaria based on a patient reported pruritus/hive score.
 | 
 • A patient reported pruritus/hive score • Patient reported pain associated with the urticaria flair based on visual analog scale (VAS) • An investigator-rated extent of urticaria; % of body area with urticaria • An investigator-rated erythema score |
| Secondary | |
| To assess the safety and tolerability of ARS-1 in subjects with urticaria after IN administration of epinephrine. | 
 • AEs • Vital signs |
| [REDACTED] | |
| [REDACTED] | |

3.0 STUDY DESIGN

3.1 Description of Study Design

This is a Phase 2, single-dose, randomized, placebo-controlled, crossover study that will consist of a screening period and an open-label treatment period. Subjects enrolled will have acute urticaria with known etiology or have chronic spontaneous urticaria with unknown etiology at least two (2) times a week while on a chronic treatment.

Each subject will be randomized to receive either a single treatment of ARS-1 (1 mg and 2 mg dose) or placebo nasal spray and then will be crossed over to receive other treatments during an acute urticaria flare. Efficacy will be primarily assessed using a patient reported pruritus/hive score and VAS for pain. Clinical assessments will also be conducted by the Investigator after dosing ARS-1.

██████████ eligible male or female subjects, 18 to 65 years of age, with urticaria who experience acute flares while on a chronic treatment regimen or chronic spontaneous urticaria with unknown etiology at least two (2) times a week will be randomized to receive ARS-1 (1 mg dose), ARS-1 (2 mg dose), or placebo. After screening subjects will return to the clinical site when experiencing an acute flare of urticaria symptoms or chronic spontaneous urticaria.

Screening Period: Subjects will be screened to assess eligibility for the clinical trial. All subjects will undergo safety screening evaluations within 90 days prior to treatment.

Open-Label Treatment Period: Subjects will return to the site when experiencing an acute flare of urticaria symptoms or chronic spontaneous urticaria before taking other acute medications. Urticaria symptoms and severity will be assessed based on both patient-reported and clinician-based assessments. After baseline safety assessments, subjects will be randomized to receive the following treatments at each of the three Treatment Periods:

- 1 mg per 100 µL dose of ARS-1,
- 2 mg per 100 µL dose of ARS-1, or
- placebo (100 µL)

If possible, rescue medication should be avoided for 15 minutes after dosing. Subjects will be monitored for both safety and symptom relief. Safety assessments will be performed after dosing and will include AEs and vital signs. Concomitant medications will be recorded.

Subjects should remain in the clinic as below:

- Acute flare: at least 2 hours after dosing and can discharge when the discharge criteria is met (the time when symptoms of acute urticaria have been effectively treated based on the investigator's or his/her designee's opinion will be recorded, not necessarily when

subjects discharged). If no relief of pruritus symptoms after 2 hours, other acute interventions may be administered as rescue.

- Chronic spontaneous urticaria: until the urticaria symptoms returns to the baseline.

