| | To determine the effect of ARS-1 versus placebo based on a patient reported pruritus/hive score | 
A patient reported pruritus/hive scorePatient reported pain associated with the urticaria flair based on visual analog scale (VAS) |
| | To assess time to effect and duration of effect on acute flares associated with urticaria based on a patient reported pruritus/hive score. | 
An investigator-rated extent of urticaria; % of body area with urticariaAn investigator-rated erythema score |
| | Secondary | |
| | To assess the safety and tolerability of ARS-1 in subjects with urticaria after IN administration of epinephrine. | 
Adverse events (AEs)Vital signs |
| | [REDACTED] | |
| Study Design | This is a Phase 2, single-dose, randomized, placebo-controlled, crossover study that will consist of a screening period and an open-label treatment period. Subjects enrolled will have acute urticaria with known etiology or have chronic spontaneous urticaria with unknown etiology at least two (2) times a week while on a chronic treatment. | |
| | Each subject will be randomized to receive either a single treatment of ARS-1 (1 mg and 2 mg dose) or placebo nasal spray and then will be crossed over to receive other treatments | |

| | |
|--------------------------------|---|

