3.2 Study Drugs

3.2.1 Test Product

ARS-1 is a solution formulation of epinephrine intended for nasal administration.

ARS-1 will be administered by IN administration using the commercial sprayer device at a dose of 1 mg and 2 mg epinephrine per spray delivered in a volume of 100 μ L aqueous solution.

Placebo is saline to be administered by IN administration using the commercial sprayer device delivered in a volume of 100 μ L aqueous solution.

Dosing will be conducted according to the Instructions for Use (IFU) ([Appendix B](#)).

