12.2 Formulation, Packaging, and Labeling

[REDACTED] single label panel
containing the following information:

ARS-1 (Intranasal Epinephrine)
Single-Use Spray
1.0 mg (100 µL at 10 mg/mL)
Lot Number: XXXXXXXX
Manufacturing Date: MMMYYYYY
Storage Conditions: Protect from light – store in package until ready to use

OR

ARS-1 (Intranasal Epinephrine)
Single-Use Spray
2.0 mg (100 µL at 20 mg/mL)

Lot Number: XXXXXXXX

Manufacturing Date: MMMYYYYY

Storage Conditions: Protect from light – store in package until ready to use

[REDACTED]

[REDACTED]

[REDACTED]

[REDACTED]

[REDACTED]

[REDACTED]

[REDACTED]

full Good Manufacturing Practice (GMP) conditions.

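### The treatment period is open-label and no readable text describes masking, so each ARS-1 versus placebo difference on patient- and investigator-rated scores mixes drug effect with expectation

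*Combined protocol and SAP*

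**What the plan says.** Section 3.1 says: "This is a Phase 2, single-dose, randomized, placebo-controlled, crossover study that will consist of a screening period and an open-label treatment period". The Study Design row of the synopsis uses the same wording, and both places head the period itself as open-label. In Section 3.1 the heading begins "Open-Label Treatment Period: Subjects will return to the site when experiencing an acute flare".

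On endpoints, Section 3.1 says: "Efficacy will be primarily assessed using a patient reported pruritus/hive score and VAS for pain". Section 2.1 sets the primary objective as ARS-1 against placebo on the patient-reported score. Its primary block also lists pain VAS, investigator-rated extent and "An investigator-rated erythema score". The time at which an acute flare counts as effectively treated is the opinion of the investigator or designee (Sections 3.1 and 10.3).

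On the products, Section 3.2.1 says: "Placebo is saline to be administered by IN administration using the commercial sprayer device". All three treatments are given in 100 µL from the commercial sprayer. The two ARS-1 label panels visible in Section 12.2 print the product name and strength. Section 3.1.1 gives two sequences, both with placebo in Period 2.

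On analysis, Section 14.3.1 tests superiority of each dose over placebo at each timepoint at two-sided 0.05. The synopsis (Statistical Analysis) applies no multiplicity adjustment and calls all analyses exploratory.

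**The concern.** In a comparison with placebo on self-rated symptoms, the placebo is there in part to equalise what subjects and raters expect. If both know that a given spray is saline, that function is lost. A subject who knows the treatment scores itch and pain. An investigator who knows it scores extent and erythema and judges when the flare has been effectively treated. Time to effect and duration of effect in Section 14.3.1 are derived from the same kind of grades.

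What is at stake is the meaning of the primary comparison. A positive ARS-1 versus placebo result could come from the drug, from expectation, or from both. No analysis of the collected data could separate them, because knowledge of treatment coincides exactly with treatment. The planned mixed model has terms for treatment, period and subject only.

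**Working it through.** There is no figure in the plan to reproduce. Section 14.1 bases the sample size on practical consideration, and no effect size, SD or power is readable.

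**1. Is masking described anywhere?** The open-label wording is consistent in the synopsis and Section 3.1. No readable text describes masking of subjects, dosing staff or raters, a matched placebo, coded kits or a code-break. Part of Section 12.2 is redacted and Sections 12.3 to 12.5 are not in the readable text. A masking statement there cannot be excluded, but it would contradict the readable wording.

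**2. How exposed is each measure?**
- Itch (0 to 3) and pain VAS are pure self-report and the most exposed.
- The hive score is a banded count (none, 1-6, 7-12, >12) and extent is a three-band grade of body surface area. Both are less exposed.
- Erythema is a 0 to 4 judgement by a rater not described as masked.
- The 1 mg versus 2 mg comparison is active against active and the least exposed.

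**3. How large could the effect be?** Inputs:
- n = 32 (synopsis) and two-sided 0.05 (Section 14.3.1).
- True drug effect set to 0.
- Expectation shift b and within-subject SD (SDw, on the 0 to 3 scale): both assumed.
- All 32 subjects contribute to the contrast, and the design allows it to be estimated.

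SE of a treatment difference = SDw × √(2/32) = SDw × 0.25, which is 0.15 for SDw 0.6 and 0.25 for SDw 1.0. Noncentrality = b / SE. Degrees of freedom = 96 observations − 32 subjects − 2 treatment contrasts = 62, with critical value 2.00.

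| Assumed shift (points) | Noncentrality, SDw 0.6 | Rejection rate | Noncentrality, SDw 1.0 | Rejection rate |
|---|---|---|---|---|
| 0 | 0 | 5% | 0 | 5% |
| 0.1 | 0.67 | 10% | 0.40 | 7% |
| 0.2 | 1.33 | 26% | 0.80 | 12% |
| 0.3 | 2.00 | 50% | 1.20 | 22% |
| 0.5 | 3.33 | 91% | 2.00 | 50% |

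Taking off two more degrees of freedom for period (60) leaves the rounded figures essentially unchanged. A paired test with 31 degrees of freedom lowers them by less than 1.5 percentage points. The rates are per comparison.

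**4. Would changing the word be enough?** Placebo is in Period 2 in both sequences, so anyone who knows the protocol knows which visit is placebo. The fixed-effects matrix (intercept, two period columns, two treatment columns) for these two sequences has rank 4 of 5. The placebo column coincides with Period 2, so neither placebo contrast is estimable with period in the model; only 1 mg versus 2 mg is. With all six treatment orders the rank is 5 and both placebo contrasts are estimable.

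**The case against.** The best defence is that open-label is a declared choice in a small Phase 2 study, sized on practical grounds, whose analyses are all called exploratory. A stated limitation might then be enough. This has some force: the exploratory label narrows what may be claimed. But Section 14.3.1 still tests superiority over placebo, and the label does not take the bias out of the estimates.

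Second, masking might be incomplete anyway. Saline lacks the absorption-enhancing excipient described in Section 1.1, so nasal sensation may differ. Vital signs are read repeatedly after dosing (Section 9.3), and Section 1.2.2 treats blood pressure and pulse as pharmacodynamic measures of ARS-1. This stands as a limit on what blinding can achieve. It is not a reason to plan full disclosure.

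Three stronger readings are tempting and should be resisted:
- A reader might infer that an open placebo serves no purpose. Section 1.1 says lesions typically clear within one to twenty-four hours, so a saline period can in principle control for spontaneous resolution. Section 3.1.1 also places it between the active doses for wash-out. In this plan the first of these controls is undercut by the fixed Period 2 placement, which is a separate fault.
- A reader might infer from Section 12.2 that the kits are visibly different. Only the two ARS-1 panels are visible, in a partly redacted section, and no placebo label can be seen. The open-label wording carries the point, not the labels.
- A reader might infer that all endpoints are equally compromised. The banded scores are less open to expectation than itch and pain.

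**Conclusion.** The point holds. As written, every ARS-1 minus placebo difference in the primary block is drug effect plus any expectation effect in subject or rater, and a positive result could not be attributed to the drug alone. The bias is likely to be greatest for itch and pain VAS, smaller for hive count and extent grade, and least for the comparison between doses.

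The size is unknown. The rates in the table, from about 7% to 91% over shifts of 0.1 to 0.5 points, depend on an assumed shift and an assumed SD, neither of which is in the documents. At the smallest shift the inflation is modest (10% to 7%). A reader might take the table as the error rate of the planned analysis. It is not: with the sequences in Section 3.1.1 and period in the model, the placebo contrasts cannot be estimated at all.

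The conclusion also rests on the readable text. If open-label is a wording error, the protocol must say so and describe who is masked and how.

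**What to change.** - In the synopsis and Section 3.1, replace open-label with double-blind and state who is masked: subjects, dosing staff, and patient and investigator raters.
- Supply the three 100 µL sprays as identically labelled coded kits per sequence. The shared sprayer and volume, and dosing by clinic staff, make this practicable.
- Keep the sequence list from subjects, dosing staff and raters, and add an emergency code-break procedure.
- Make this change together with sequences that spread placebo over the three periods, for example all six orders. A fixed Period 2 placebo reveals itself and is aliased with period. Section 3.1.1 gives wash-out as the reason for the present order, so that statement must be reconciled with the new sequences.
- State as limitations that saline lacks the excipient and that post-dose blood pressure and pulse changes may partly unmask treatment.

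The cost is kit relabelling, a code-break procedure and a revised randomisation scheme, with masking that may still be incomplete. The masking itself does not call for more subjects or more treatment periods; any effect of the new sequences on the wash-out arrangement would have to be worked out by the sponsor.

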3.1.1 Randomization/Assignment to Study Drug

subjects with urticaria who experience acute flares while on a chronic treatment regimen or chronic spontaneous urticaria with unknown etiology at least two (2) times a week will be enrolled and randomized to receive the following treatments in each Treatment Period:

- 1 mg/100 μ L dose of ARS-1,
- 2 mg/100 μ L dose of ARS-1,
- placebo

To ensure proper wash-out between the IN doses, each subject will be randomized to one of the following sequences:

- 1 mg ARS-1 IN: placebo: 2 mg ARS-1 IN
- 2 mg ARS-1 IN: placebo: 1 mg ARS-1 IN

The side (right or left) of dosing will be alternated per randomization.

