10.3 Drug Administration

After baseline safety assessments, subjects will be randomized to receive the following treatments at each of the three Treatment Periods:

- 1 mg per 100 μ L dose of ARS-1,
- 2 mg per 100 μ L dose of ARS-1, or
- placebo (100 μ L)

ARS-1 or placebo will be dosed to the nostril by the medical professional in a clinical setting per IFU ([Appendix B](#)). [REDACTED]

[REDACTED] Subjects will be monitored for both safety and symptom relief. Safety assessments will be performed after dosing and will include AEs and vital signs. Concomitant medications will be recorded.

Subjects should remain in the clinic as below:

- Acute flare: at least 2 hours after dosing and can discharge when the discharge criteria is met (the time when symptoms of acute urticaria have been effectively treated based on the investigator's or his/her designee's opinion will be recorded, not necessarily when subjects discharged). If no relief of pruritus symptoms after 2 hours, other acute interventions may be administered as rescue.

- Chronic spontaneous urticaria: until the urticaria symptoms returns to the baseline. [REDACTED]

The calendar date and 24-hour clock time of all doses will be recorded on the eCRF.

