Appendix B: Instructions for Use

| INSTRUCTIONS FOR USE neffy Epinephrine Nasal Spray (Single-Use) Use Only In Nose | | |
|---|--|--|
| 
neffy Nasal Spray device is for the emergency treatment of allergic reactions including anaphylaxis.
 
Read this Instructions for Use on how to use neffy.
 
Ask a healthcare provider if you have any questions on how to use neffy.
 
As you may require more than 1 dose, carry 2 neffy Nasal Spray devices with you whenever possible.
 
Your neffy Nasal Spray device:
  
Important Information:
 
 • Use only in the nose. Avoid spraying in the eyes or mouth. • Do not test or prime (pre-spray); each neffy can only be sprayed 1 time. • Each neffy Nasal Spray device contains only 1 dose and is for single-use only. Do not reuse. • Check your neffy periodically to be sure the expiration date has not passed. Replace your neffy before the expiration date has passed. • Contact a medical professional after using neffy to determine if more medical care is needed. | 
Dosing neffy Nasal Spray device
 
1A  Remove neffy from packaging (see Figure 1A). Pull open the packaging to remove the neffy Nasal Spray device.
 
1B  Hold device as shown (see Figure 1B). Hold the device with your thumb on the bottom of the plunger and a finger on either side of the nozzle. 
 • Do not pull or push on the plunger. • Do not test or pre-spray; each device has only 1 spray. 
 
1C  Insert tip of sprayer into a nostril until your fingers touch your nose (see Figure 1C). Keep the nozzle straight into the nose pointed toward your forehead. Do not angle the sprayer to the septum wall or outer wall of the nose.
 
1D  Press plunger up firmly until it snaps up and sprays into the nostril (see Figure 1D). If any error is made in dosing or any liquid drips out of the nose, repeat dosing with a second neffy Nasal Spray device.
 
⚠ Do not angle sprayer Do not angle the sprayer to the septum wall or outer wall of the nose.
 

 
+ Contact a medical professional after use Contact a medical professional to determine if more care is needed. Tell them that a neffy Nasal Spray has been used.
 | 
⌚ After 10 minutes, repeat dosing, if necessary Monitor patient for symptoms. If symptoms get worse or reoccur after 10 minutes, or if any error in dosing, use a new neffy Nasal Spray device to give a 2nd dose in the other nostril.
 
Disposing of used neffy Nasal Spray device:
 
 • Dispose of used neffy Nasal Spray device in household trash. • Do not recycle.  
Store neffy Nasal Spray in the blister pack provided.
 
 • Store below 77°F (25°C). Excursions permitted up to 122°F (50°C). • Allow to thaw for 20 minutes if inadvertently frozen. • neffy Nasal Spray freezes at temperatures below 5°F (-15°C). If this happens, the device will not spray. If neffy Nasal Spray is inadvertently frozen and is needed in an emergency, do NOT wait for neffy Nasal Spray to thaw. Get emergency medical help right away. However, neffy Nasal Spray may still be used if accidentally frozen by thawing it at room temperature for 20 minutes. 
Additional Information: Call [contact]
 
ARS Pharmaceuticals, Inc. [name]
 |

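### No efficacy score is tied to rescue and no rule covers scores taken after it, so in an open-label crossover relief from rescue is credited to the assigned treatment

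*Combined protocol and SAP*

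**What the plan says.** **When rescue may be given.** Section 3.1 and the synopsis say "If possible, rescue medication should be avoided for 15 minutes after dosing". For acute flares, sections 3.1 and 10.3 add "If no relief of pruritus symptoms after 2 hours, other acute interventions may be administered as rescue". No score threshold defines relief. For chronic spontaneous urticaria the readable text says only how long the subject stays in the clinic.

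**Who knows the treatment.** The trial "will consist of a screening period and an open-label treatment period". Section 3.1.1 gives two sequences, "1 mg ARS-1 IN: placebo: 2 mg ARS-1 IN" and "2 mg ARS-1 IN: placebo: 1 mg ARS-1 IN". Placebo is in Period 2 in both.

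**When scores are taken.** Sections 3.3 and 6.0 and the Appendix A footnotes set scores before dosing, at 5, 10, 15, 30, 45, 60 and 120 minutes, and hourly thereafter, each with a window. The actual time of each assessment is recorded. No readable item asks for a score because rescue is about to be given.

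**What is recorded about rescue.** An Appendix A footnote has rescue use recorded at the discharge assessment. Rescue also meets the definition of concomitant medication in 3.5.1, which is collected after dosing (10.4) and at discharge (10.5). The clock-time requirement in 10.3, "The calendar date and 24-hour clock time of all doses will be recorded on the eCRF", sits in the section on giving study drug.

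**How scores are analysed.** Section 14.3.1 compares each ARS-1 dose with placebo at every timepoint. It defines time to effect by drops of one, two and three grades. The synopsis model has terms for treatment, period and subject. Neither mentions rescue.

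**The concern.** A subject rescued at, say, 70 minutes still has a 120-minute score. That score reflects the rescue drug as well as the study treatment, yet it enters the dose-versus-placebo contrast like any other. If it is a grade lower, the drop also counts toward time to effect for whatever was sprayed in that period.

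This would matter less if rescue were equally likely in every period. Here staff can know which visit is placebo, and early rescue is only softly discouraged, so rescue may well differ by treatment.

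Effect versus placebo, time to effect and duration are all primary objectives. If neither a pre-rescue score nor a rescue time is collected, no later analysis can separate relief before rescue from relief after it.

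**Working it through.** There is no planned figure to reproduce: section 14.1 rests the sample size on practical grounds, and no rescue rate or effect is readable. Two things can be worked out.

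**1. Age of the last score before rescue.** Inputs are the schedule and windows in 3.3. The nominal gap is the difference between planned times. The largest gap runs from the earliest allowed time of one score to the latest allowed time of the next.

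| Interval (min) | Nominal gap (min) | Largest gap with windows (min) |
|---|---|---|
| 15 to 30 | 15 | 35 − 12 = 23 |
| 30 to 45 | 15 | 50 − 25 = 25 |
| 45 to 60 | 15 | 70 − 40 = 30 |
| 60 to 120 | 60 | 130 − 50 = 80 |
| 120 to 180 | 60 | 190 − 110 = 80 |

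Up to 60 minutes the last score is therefore at most 15 minutes old (30 with windows). After that it can be 60 minutes old (80 with windows).

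If rescue times are spread evenly, which is an assumption, the mean age is half the gap:

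- rescue at 15–60 minutes: 15/2 = 7.5 minutes
- rescue at 60–120 minutes or between hourly scores: 60/2 = 30 minutes
- rescue anywhere in 15–120 minutes: (45 × 7.5 + 60 × 30)/105 = 2137.5/105 = 20.4 minutes

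A score taken just before rescue brings this to about zero.

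**2. Effect on a contrast (illustration only).** Of the seven post-dose scores through 120 minutes, four (30, 45, 60 and 120) fall after the 15-minute request and can follow rescue. With scores used as observed:

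observed contrast = true contrast − (share rescued on placebo − share rescued on ARS-1) × extra relief from rescue

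Every input below is assumed: a true contrast of 0.50 points and 1 point of extra relief.

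| Rescued, placebo | Rescued, ARS-1 | Observed contrast |
|---|---|---|
| 20% | 20% | 0.50 − 0.00 = 0.50 |
| 20% | 5% | 0.50 − 0.15 = 0.35 |
| 30% | 10% | 0.50 − 0.20 = 0.30 |
| 50% | 10% | 0.50 − 0.40 = 0.10 |
| 10% | 20% | 0.50 + 0.10 = 0.60 |

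More rescue on placebo shrinks the contrast, more on ARS-1 enlarges it, and equal rescue leaves it unchanged. The table shows the mechanism; it does not estimate what will happen in this trial.

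**The case against.** **The 2-hour sentence may be the intended trigger.** Section 3.6 keeps subjects in the clinic for at least 2 hours to complete assessments. On this reading little rescue occurs before 120 minutes, and a score is due then. This has weight: a reader might infer that the plan hands the middle period to staff discretion, but that would be an inference from silence. Still, the sentence permits late rescue without barring early rescue, covers acute flares only, and would leave the 15-minute request without a purpose if nothing were allowed before 2 hours.

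**Scores already fall at the two named times.** This is true, and it narrows the concern to rescue at other times, chiefly after 60 minutes. It would also be a stretch to say that the 15-minute score is generally contaminated. Its window runs to 18 minutes, but staff would have to give rescue before taking a score already due.

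**Rescue is captured.** It is recorded as rescue and as concomitant medication, and a form may well collect the time. A reader should not infer that the data are absent. What is missing from the readable text is a requirement for the clock time and for a score tied to it.

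**Redactions.** Section 3.5.2, parts of 10.3 and 10.4, rows and footnotes of Appendix A, and section 14.5 are blacked out. Any of them may hold a rule. The analysis text in 14.3.1 and the synopsis statistics show no redaction.

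**The analyses are exploratory.** This limits the claims that can be made, but these contrasts remain the trial's efficacy result.

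**A second spray.** A reader might infer from the Instructions for Use in Appendix B that repeat dosing adds to the problem. The trial is described as single-dose, so nothing is built on this.

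**Conclusion.** The point holds as a worthwhile, low-cost improvement. In the readable text, rescue before 2 hours is not barred, the treatment is known, no score is tied to rescue, no clock time for it is required, and 14.3.1 credits any later relief to the assigned treatment. The measurable part is the age of the last clean score: up to 60 minutes after the first hour, or 80 with windows.

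The documents do not support a claim that the result will be biased by a given amount or in a given direction. With scores as observed, more rescue on placebo works against ARS-1; with rescue counted as failure, it works in favour of ARS-1. For duration, the literal definition starts when the grade rises above baseline. Rescue would lengthen it only if the span of improvement is meant.

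The conclusion assumes that the redacted sections contain no rescue rule. If they do, the sponsor can settle the point by citing it.

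**What to change.** In 3.3, 6.0, 10.4 and the Appendix A footnotes on the scores, add:

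> The itch/hive score, VAS and investigator ratings are taken immediately before any rescue, without delaying care; the clock time of and reason for rescue are recorded.

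In 14.3.1, add:

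> A grade reduction first seen after rescue does not count toward time to effect (the subject is counted as not reaching that reduction in that period), and duration of effect ends at rescue. As a sensitivity analysis of the timepoint contrasts, scores after rescue are replaced by the pre-rescue score, or by the last scheduled score if none was taken, and reported beside the as-observed analysis, with the number rescued and time of rescue by treatment.

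The cost is wording in five sections, one unscheduled set of scores, one eCRF entry for time and reason, and one extra analysis. No treatment is withheld. Scoring takes about a minute before rescue, and some pre-rescue scores will be missing when care is urgent. The replacement is a single imputation and understates uncertainty, which is why it is a sensitivity analysis. Any treatment-related difference in how readily rescue is given will remain; the change makes it visible.
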